1.5.4 Incidence and Severity of Rejection and Anti- Donor Reactivity

These endpoints will be assessed at 52 weeks post-transplant. Biopsy grading and antibody assessments will be performed at the CTOT-15 Core Laboratories.

- 1. The incidence and severity of acute cellular rejection defined by the Kidney Banff 2007 criteria and Pancreas Banff 2011 criteria within the first 52 weeks.
- 2. The severity of first and highest grade of acute cellular rejection in the renal and pancreas biopsies
- 3. The incidence of humoral rejection in the renal and pancreas biopsies.
- 4. The prevalence of *de novo* anti-donor antibodies and anti-HLA antibodies.
- 5. The type of treatment of rejection.

1.5.5 Safety Outcome Measures

The following safety outcome measures will be assessed:

- 1. The incidence of death, graft loss, or undetectable c-peptide.
- 2. The incidence of all adverse events (AEs) and serious adverse events (SAEs).
- 3. The incidence of selected AEs and SAEs including:
 - Infections requiring hospitalization or systemic therapy,
 - BK and CMV viremia (local center monitoring),
 - EBV Infection (local center monitoring),
 - Malignancy.

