enroll in the pregnancy registry. The patient should also be apprised of the potential hazard of mycophenolate products to the fetus. The risks and benefits of CellCept/Myfortic should be discussed with the patient. In certain situations, the patients and her healthcare practitioner may decide that the maternal benefits outweigh the risks to the fetus.

If following initiation of study treatment, it is subsequently discovered that a subject is pregnant or may have been pregnant at the time of investigational product exposure, including during at least 56 days after product administration, the investigational product will be permanently discontinued.

Protocol-required procedures for study discontinuation and follow-up must be performed on the subject unless contraindicated by pregnancy (e.g., x-ray studies). Other appropriate pregnancy follow-up procedures should be considered if indicated. In addition, the investigator must report on the appropriate follow-up information regarding the course of the pregnancy, including perinatal and neonatal outcome. Infants should be followed for a minimum of 8 weeks. This pregnancy surveillance procedure includes male subjects who fathered a child while receiving study medication; however, male subjects do not need to discontinue study medication.

Viral Monitoring

The local center will monitor all subjects for CMV and BKV infection by quantitative PCR in the blood. This monitoring will take place at days 28 and 84, and at weeks 28, 52 and 76. The local center investigators will make all treatment decisions.

For Cause Biopsies - Renal

The center will perform a biopsy per the discretion of the Investigator in cases of increase in serum creatinine, proteinuria, or other clinical symptoms.

The local center will send the Pathology Core Lab ([name], UCSF) the following:

- 5 original stained slides (1-Trichrome or unstained, 1-PAS, 3 H&E) for histology reading.
- The site will send 1 SV40 and 1- immunohistochemistry C4d stained slides, if collected as standard of care.
- The remaining portion of the FFPE block will be stored at the local center and sent to the Core Pathology when requested for additional immunohistochemistry studies.

The local center will send the Molecular Core Lab ([name], University of Alabama) the following:

• 1 core in RNALater for gene expression, mRNA profiling studies.

Standard of Care or For Cause Biopsies- Pancreas

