12 MECHANISTIC ASSAYS

As discussed in other sections of the protocol, we propose that the substitution of belatacept for tacrolimus will result in better preservation of renal function. However, the results of the phase II and phase III studies conducted to date suggest that belatacept, at least as used in those studies, may be associated with a slightly increased risk of acute alloimmune-mediated graft injury and an increased risk of PTLD, which is most commonly a consequence of an active EBV infection. Consequently, our areas of focus include determinations of renal function, viral infections, and alloimmunity. Mechanistic assays will be paired with clinical measurements in an attempt to gain insights into the mechanisms responsible for the hypothesized differences between the 2 treatment groups.

Study participants will be informed that they may be approached about additional clinical evaluations or studies that have received the full approval of the NIAID as new evaluations are identified. If additional evaluations or studies are determined to be desirable, this protocol (and other appropriate study documents, (e.g., the informed consent and the statistical analysis plan) will be amended and submitted to the appropriate regulatory authorities, ethics committees, and IRBs for approval. Each participant's signature will be obtained on the revised informed consent form before additional evaluations are performed. The specimens from these evaluations may be stored up to the end of the grant – approximately 5 years, or longer if the grant is extended.

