12.8 Viral Testing

Viral infection following renal transplantation remains a significant source or recipient morbidity and mortality as well as a significant cause of allograft dysfunction and loss. We will test and quantify the presence of viremia. These tests will be completed in batch assay runs by a core laboratory, and results will not be available to the clinical centers. Detection of the following viruses will be performed by single assay Quantitative PCR: CMV, BKV, JCV, HHV6 and HHV7. EBV will be performed on serum. In collaboration with the Emory Clinical Laboratories we are developing quantitative viral load assays for HHV3 (varicella zoster), HHV6 (roseola), HHV7 (a potential co-factor for CMV disease), polyoma JC and the recently described polyoma WC and KI viruses. If cost-effective multiplexed or low-density arrays are developed, we will consider extending our studies to map the patterns of reactivation and viremia with these latent/chronic viruses.

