Appendix 1: Schedule of Events – Pre-Transplant to Day 4 Post-Transplant (Visit 1)

Screening Assessments	Window
 Blood Type (A, B, O), Rh Factor HLA Typing (Class I: A, B, C, Class II: DR, DP, DQ) Peak PRA, Current PRA or cPRA (within 12 months prior to transplant), Crossmatch Hepatitis B, Hepatitis C, and HIV test results Last reported CMV (IgG, IgM and/or total CMV Ab) and EBV testing (IgG, IgM) Tuberculosis testing (within 12 months prior to transplant). If documentation is not present at the time of transplant, and the subject does not have any risk factors for TB, a TB-specific interferon gamma release assay (IGRA) may be performed. 	Retrospective data collection, no time limits unless specified. Repeat only if not available.
 Informed Consent and Assessment of Eligibility Demographics Medical History, Physical exam (BP, Pulse, Temperature, Respiration, Weight) Concomitant Medications Local Labs: Serum Pregnancy Test, Hematology Panel (CBC, differential, platelets), Chemistry 12-Panel / CKD-EPI equation, MDRD 4 variable, Serum Amylase, Serum Lipase, Fasting Lipid Panel (Total, HDL, LDL, Triglycerides), Hemoglobin A1c, Urinalysis 	Within 30 days prior to transplant, until time of transplant.
 Flow Cytometry (20mL blood in Cyto-Chex Tube) Intracellular Cytokine Staining – Viral Phenotyping (32mL blood in CPT Tube) Markers of Autoimmunity – PBMC (30mL blood in Green-top Tube) Markers of Autoimmunity – serum (5mL blood in Red-top Vacutainer) Gene Expression, mRNA profiling in blood (2.5 mL blood in PAXgene RNA tube) Cytokines and Growth Factors- serum (7mL blood in Red-Top Vacutainer) Serum Proteins – CTGF, TGFbeta (4.5mL blood in CTAD) Urine Proteins – CTGF, TGFbeta (supernatant) Gene Expression, mRNA profiling in urine (urine pellet) Non-HLA Ab, Anti-HLA Ab, DSA (5mL blood in Red-top Vacutainer) Genomics- gene polymorphisms (4mL in Lavender-top EDTA Vacutainer) Viral Monitoring by PCR (CMV, BKV, JCV, HHV6, HHV7) and Viral Assay Development (HHV3- varicella zoster, HHV6- roseola, HHV7- cofactor CMV, polyoma JC, WC, KI).(plasma from ICS sample) 	Within 48 hours prior to transplant
 Randomization (RhoRand System) Assessment of Events: AE/SAE Solumedrol®(Methylprednisone) : 500mg – Intraoperatively Thymoglobulin® (Anti-thymocyte Globulin – Rabbit) Prograf® (tacrolimus) CellCept® (mycophenolate mofetil) 	Day of Transplant
 Methylprednisolone 250 mg Thymoglobulin® (Anti-thymocyte Globulin – Rabbit) 	Day 1 Post-Transplant

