Appendix 2. Schedule of Events (Recipient) Post-Transplant

		DAYS			WEEKS												
		5	14	28	56	84	16	20	24	28	32	36	40	44	48	52	FOR CAUSE
	VISIT NUMBERS	2	3	4	5	6	7	8	9	10	11	12	13	14	15	16	2, 3
	VISIT WINDOWS (+/- DAYS)		2	3	3	3	3	3	3	5	5	5	5	5	5	5	_, -
	RAL ASSESSMENTS																
Physical Exam	BP, Pulse, Temperature, Respiration, Weight	Х	Х	Х	Х	Х	Х	Х	Х	Х	Х	Х	Х	Х	Х	Х	
Immunosuppressive Meds	Drug Name and Dose	\rightarrow	\rightarrow	\rightarrow	\rightarrow	\rightarrow	\rightarrow	\rightarrow									
Concomitant Medications	Drug Name (Anti-HTN, Prophylaxis, Anti-Viral)	Х	Х	Х	Х	Х	Х	Х	Х	Х	Х	Х	Х	Х	Х	Х	Х
Assessments of Events	AE/SAE, Infections, Rejections, Hospital, Graft Loss, Malignancies, New Onset Diabetes, Death	\rightarrow	\rightarrow	\rightarrow	\rightarrow	\rightarrow	\rightarrow	\rightarrow									
Neurological Assess. for PML	Hx, mini mental, cranial nerve, motor, cerebellar			Х		Х				Х		Х				Х	
	LOCAL LABO	RAT	ORY	ASS	SESSI	MEN	TS										
Hematology Panel	CBC, differential, Platelet			Х		Х				Х		Х				Х	Х
Chemistry Panel / GFR (CKD-EPI and MDRD)- Renal Function	Serum Creatinine, BUN, glucose, sodium, AST, ALT, ALP, bilirubin, albumin, calcium, phosphate			X		Х				X		Х				X	Х
Chemistry- Pancreatic Function	Serum Amylase, Serum Lipase			X		X				X		X				X	Х
Fasting Lipid Panel	Total, HDL, LDL, Triglycerides									Х						Х	
C-Peptide	C-Peptide															Х	Х
Hemoglobin A1c	HbA1c			Х		Х				Х		Х				Х	
Urinalysis	Protein, Glucose, Hematuria, WBC			Х		Х				Х		Х				Х	Х
Trough Levels	Tacrolimus trough levels	Х	Х	Х	Х	Х	Х	Х	Х	Х	Х	Х	Х	Х	Х	Х	Х
Viral Monitoring	BKV and CMV by PCR in blood			Х		Х				Х						Х	
Histology- Renal	Local Read- Banff 2007 Renal																Х
Histology – Pancreas	Local Read- Banff 2011 Pancreas																Х
	NULOJIX® (BELA	ГАС	EPT)	INF	USIO	N D	OSIN	IG			. 			1			
Belatacept Infusion Investigational Arm 	IV, 10mg/kg	X4	X	X	X	X											
Belatacept Infusion Investigational Arm 	IV, 5mg/kg						Х	Х	Х	Х	Х	X	Х	Х	Х	Х	
TACROLIMUS DOSING SCHEDULE																	
Tacrolimus Dosing Control Arm 	Dose adjusted to target trough levels of 8- 12ng/mL to week 24, then 5-8ng/mL thereafter.	\rightarrow	\rightarrow	\rightarrow	\rightarrow	\rightarrow	\rightarrow	\rightarrow									
Tacrolimus Dosing ^{6,7,8} Investigational Arm 	Dose adjusted to target trough levels 5-8 ng/mL to week 24, then 3-5 ng/mL until week 40.	\rightarrow	\rightarrow	\rightarrow	stop												

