MYCOPHENOLATE MOFETIL DOSING SCHEDULE																	
Mycophenolate Mofetil	1gm BID, Adjusted based on clinical complications	\rightarrow	\rightarrow	\rightarrow	\rightarrow	\rightarrow	\rightarrow	\rightarrow									

Optimization of Belatacept Usage as a Means of Minimizing CNI Exposure in Simultaneous Kidney and Pancreas Transplantation Version 6.0/ May 14, 2015

Page 98 of 104

		DAYS			WEEKS												
		5	14	28	56	84	16	20	24	28	32	36	40	44	48	52	FOR
	VISIT NUMBERS	2	3	4	5	6	7	8	9	10	11	12	13	14	15	16	CAUSE [,]
	VISIT WINDOWS (+/- DAYS)		2	3	3	3	3	3	3	5	5	5	5	5	5	5	3
CELLULAR CORE LABORATORY- EMORY UNIVERSITY (PI: [name]																	
Intracellular Cytokine Staining	32 mL Blood CPT Tube									Х		X				Х	Х
Flow Cytometry	20-40 mL Blood Cyto-Chex Tube			Х		Х				Х		Х				Х	Х
MA	RKERS OF AUTOIMMUNITY COR	E LAI	BOR	ATO	RY- L	JCSF	F (PI:	[name], M	D)					
Markers of Autoimmunity- PBMC	30 mL Blood Green-Top Vacutainer			Х		Х				Х		Х				Х	Х
Markers of Autoimmunity- Serum	5mL Blood- Red-Top Vacutainer			Х		Х				Х		Х				Х	Х
MOLECULAR CORE LABORATORY- UNIVERSITY OF ALABAMA (PI: [name])																	
Gene Expression, mRNA Profiling (Blood)	2.5 mL Blood- PAXgene RNA Tube			Х		Х				Х		Х				Х	Х
Gene Expression- mRNA Profiling (Urine)	50-100 mL Urine (Pellet)			Х		Х				Х		Х				Х	Х
Gene Expression- mRNA Profiling (Tissue)	1 renal core in RNALater																Х
ASSAYS OF AL	ASSAYS OF ALLOGRAFT INJURY LABORATORY- UNIVERSITY OF ALABAMA (PI: [name])																
Cytokines and Growth Factors	7 mL Blood - Red-Top Vacutainer			Х		Х				Х		Х				Х	Х
Serum Proteins- CTGF, TGFbeta	4.5mL Blood- Light Blue CTAD			Х		Х				Х		Х				Х	Х
Urine Proteins- CTGF, TGFbeta	50-100 mL Urine (Supernatant)			Х		Х				Х		Х				Х	Х
ANTIBO	DY CORE- EMORY UNIVERSITY S	CHC	OOL	OF M	IEDI	CINE	E (PI:	[name]	, PHI	D)				
Non-HLA Ab/Anti-HLA Antibodies / DSA ¹	5 mL Blood - Red-Top Vacutainer			Х		Х				Х		Х				Х	Х
	PATHOLOGY CORE LABORAT	ORY-	- UCS	SF (P	I: [name], I	MD)	•			•	•		
Histology/Immunohistochemistry - Renal	5 slides (1-Trichrome or unstained, 1- PAS, 3-H&E) AND FFPE tissue (remaining block) AND C4d and SV40																Х
Histology- Pancreas	slides (if available) 4 slides (1-Trichrome/ unstain, 3-H&E)																Х
VIRAL MONITORING CORE- EMORY UNIVERSITY (PI: [name])																	
Viral Monitoring by PCR (EBV) AND Viral	4 mL Blood in EDTA Lavender-top			X	111	X		5 n w		X		X				X	Х

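### EBV infection is a safety outcome taken from local monitoring, but no local post-transplant EBV test is scheduled, and the blinded core-laboratory EBV PCR is not linked to it

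*Combined protocol and SAP*

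**What the plan says.** Section 1.5.5 and the synopsis include EBV infection among the selected adverse events and give its source in brackets: "EBV Infection (local center monitoring"). The safety rows of Table 9 (Section 13.2.2) plan one log-binomial or Poisson model per infectious disease, comparing the arms.

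Section 10.3 then sets the local viral monitoring: "The local center will monitor all subjects for CMV and BKV infection by quantitative PCR in the blood". It adds: "This monitoring will take place at days 28 and 84, and at weeks 28, 52 and 76". The matching local laboratory row in Appendices 2 and 3 reads "BKV and CMV by PCR in blood". Appendix 4 has the same content, reduced to CMV alone at week 52. The only local EBV test on a recipient schedule is the pre-transplant serology in Appendix 1: "EBV testing (IgG, IgM").

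After transplant, EBV PCR appears only among the core-laboratory rows of Appendix 2, as "Viral Monitoring by PCR (EBV) AND Viral" monitoring assay development. Section 12.8 says of the core viral assays: "These tests will be completed in batch assay runs by a core laboratory, and results will not be available to the clinical centers". Section 10.4.1 keeps core-laboratory personnel blinded to treatment. Table 10 gives EBV prevalence to mechanistic analysis 11a.

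**The concern.** The outcome names a source that the schedules do not supply. Detection falls back on event-driven reporting. Section 10.3 has infections assessed at each visit, but less serious outpatient infections are recorded only when diagnosed, treated and confirmed by tests the site chose to run. Section 11.3.1 limits adverse event recording to grade 2 and above. An untreated viremia without symptoms could pass unrecorded in either arm.

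EBV is not a marginal item here. Section 12 links belatacept to "an increased risk of PTLD, which is most commonly a consequence of an active EBV infection", and Section 2.1 makes avoiding an increase in viral infections a second goal of the trial. PTLD itself will be too rare to say much with 30 subjects per arm; Table 4 needs 3 cases at N = 30 to trigger its rule. EBV infection is the more frequent signal a reader will look to. Section 10.4.1 already voices concern that unblinded investigators may be biased in assessing endpoints, and an outcome that depends on who was tested is exposed to that concern.

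**Working it through.** The check is a count of scheduled tests by source, followed by a trace of each source to its planned analysis.

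**Step 1. Tests by schedule.**

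| Schedule | Local CMV/BKV PCR | Local EBV test | Core EBV PCR |
|---|---|---|---|
| Appendix 1 (visit 1) | 0 | pre-transplant serology only | 0 (core panel names CMV, BKV, JCV, HHV6, HHV7) |
| Appendix 2 (year 1) | 4: days 28, 84; weeks 28, 52 | 0 | 5: days 28, 84; weeks 28, 36, 52; plus for cause |
| Appendix 3 (year 2) | 1: week 76 | 0 | 0 |
| Appendix 4 (reduced follow-up) | CMV at days 28, 84, weeks 24, 52; BKV at the first three | 0 | 0 |

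The local CMV/BKV count for Appendices 2 and 3 is 4 + 1 = 5, which agrees with the five time points in Section 10.3. The omission of EBV is therefore consistent across the text and the tables, and is not a slip in one row.

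**Step 2. How much core data exists.** At most 5 × 60 = 300 scheduled EBV results, or 5 × 30 = 150 per arm. This is a ceiling: it assumes that all 60 subjects stay on Appendix 2 to week 52. Section 8.7 moves subjects who stop study treatment before week 52 to Appendix 4, which has no core rows.

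**Step 3. Where each source goes.** Locally reported infections feed the Table 9 safety model. Core EBV PCR feeds analysis 11a (contingency tables and CMH tests). No text joins the two. Analysis 11a is also conditional: the footnote to Table 10 allows tests only if sample sizes are adequate, and Section 13.2.3 expects testing to be restricted mainly to continuous endpoints.

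**Step 4. What site-chosen testing does to the comparison.** Let p be the true proportion with EBV viremia in an arm and t the proportion of that arm tested locally. Assume testing is unrelated to viremia within the arm and every positive is recorded. The recorded proportion is then p × t, and the recorded ratio between arms is (p_B × t_B) / (p_C × t_C), with B for belatacept and C for control. If p_B = p_C, the ratio reduces to t_B / t_C. With equal testing the ratio is unbiased, but the event count shrinks by the factor t. With unequal testing the ratio moves away from 1 with no true difference. The documents give no value for p or t in either arm, so no size or direction can be computed.

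**Step 5. Definition and specimen.** The Study Definitions define BKV infection but have no entry for EBV infection. Section 12.8 says the EBV assay is done on serum, while Appendix 2 lists an EDTA tube for it.

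**The case against.** The strongest reply has four parts.

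- **Infections are collected anyway.** They are assessed at every visit, and Appendices 2, 3 and 4 all carry that row. This stands. A reader might infer that EBV infection has no data source at all, and the documents do not support that. What is missing is a systematic local source.
- **The wording may be deliberate.** Section 1.5.5 speaks of viremia for BK and CMV but of infection for EBV, which could mean a locally diagnosed illness rather than a scheduled PCR. This is a fair reading. On it, the gap is the missing case definition and the dependence on site testing, and replacing the outcome outright with PCR positivity would change what is measured. That is why the two should be reported side by side.
- **A blinded comparison is already planned.** Analysis 11a compares core EBV prevalence by arm. This stands in part: the comparison exists, but as a conditional mechanistic analysis not tied to the safety outcome.
- **The downstream risk is watched separately.** EBV-seronegative recipients are excluded (Section 6.3), PTLD has its own stopping rule (Section 9.2.2) and malignancy is its own safety outcome. The DSMB listing in Section 11.8.2 is a minimum, so nothing bars EBV results from DSMB review. All of this stands. It limits the safety consequence but does not repair the EBV comparison.

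A reader might also infer that sites, warned about PTLD in Section 5.1, will test the belatacept arm more and so make it look worse. That is plausible, but no passage describes local EBV testing by arm. It is a risk, not a finding.

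**Conclusion.** The mismatch is real and should be corrected before analysis. The safety outcome for EBV infection rests on a local source with 0 scheduled post-transplant tests, while 5 scheduled core PCRs per subject, run blinded to arm, are left outside it. The between-arm safety comparison is open to under-ascertainment and, if testing differs by arm, to bias whose size and direction the documents do not allow one to state.

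The conclusion rests on the schedules being followed as written. If sites test for EBV routinely and equally under local practice, the bias disappears, but the plan neither requires nor records that. The core PCR is better protected from bias but incomplete: it has no visit 1 sample and no results in year 2 or in reduced follow-up. Reasons for stopping treatment in Section 8.7 include adverse events and graft failure, so the missing results may be informative.

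**What to change.** In Section 1.5.5 (and the synopsis) and the Table 9 safety row:

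1. Report EBV viremia through week 52 by arm from the core PCR already scheduled at days 28 and 84 and weeks 28, 36 and 52. State the positivity definition, and give the number of subjects tested at each visit as the denominator.
2. Report locally diagnosed EBV infections separately, labelled as event-driven, with a case definition added to the Study Definitions.
3. State the limits. Without a visit 1 PCR, viremia first seen at day 28 cannot be dated to after transplant. Results end at week 52 and are missing for subjects on Appendix 4, so show the number moved to that schedule by arm.
4. Reconcile Sections 1.5.5, 10.3 and 12.8 and the Appendix 2 rows on the data source, the specimen type (serum or EDTA tube) and who sees the results.

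The cost is wording and one additional safety table. No new samples are needed, provided the gap in reduced follow-up is accepted and stated. The change remains feasible with study completion set for August 31, 2016, because the amendment keeps subjects on their existing schedules. It should be written before results by arm are seen.

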1.6 Mechanistic Secondary Endpoints

Samples for **Mechanistic studies** will be collected as specified on the SOE.

Immune Reactivity and Function

- 1. Multiparameter flow cytometric enumeration and phenotyping of peripheral blood leukocyte subsets. (Emory Cellular Core Laboratory)
- 2. Protective immunity (Emory Viral Surveillance Core Laboratory)
 - a. Viral load monitoring EBV, CMV, Polyoma BKV & JCV
 - b. Quantity and quality of CMV- and EBV- specific T cells and viral-specific antibody.
- 3. Anti-donor responses
 - a. Donor-specific antibody (Emory HLA Clinical Laboratory).
 - b. Immunohistochemistry of for-cause renal allograft biopsies (UCSF Pathology Core Lab).
 - d. Gene expression, mRNA profiling in blood, urine and tissue (University of Alabama Molecular Core Laboratory).
- 4. Serum and urine proteins, selected biomarkers of acute and chronic kidney injury (University of Alabama Protein Assay Core Laboratory).

Page 24 of 104

2 BACKGROUND AND RATIONALE

2.1 Background

The overarching aim of CTOT-15 is to investigate a belatacept-based immunosuppressive regimen for the purpose of minimizing the dependence of subjects undergoing simultaneous kidney and pancreas on CNIs and steroids. This study will test the hypothesis that the minimization of CNI exposure and avoidance of steroids will be facilitated by a belatacept-based regimen using thymoglobulin induction. We propose that the minimization of CNIs will lead to superior renal function with comparable rates of rejection compared with a tacrolimus-based maintenance immunosuppressive regimen in recipients of SPK. A second goal is to achieve these ends without an increase in viral infections or virus-associated malignancies.

CTOT-15 is designed to complement the CTOT-16 protocol conducted in renal transplants recipients and extend a comparable line of investigation to recipients of SPK. This group is particularly underserved with respect to trials examining new immunosuppressive regimens. In fact, there have been no multicenter, randomized, prospective trials in combined pancreas and kidney transplantation since the early 1990s. Thus, immunosuppressive protocols in SPK transplantation are largely devised based on experiences with other transplanted organs and reason rather than data. Data from the 2009 Annual Report of the SRTR indicated that in patients transplanted in 2008 immunosuppressive management after SPK transplantation is far from standardized with 16 different regimens reportedly used at the time of discharge following transplantation. Induction was used in 83.4% of transplant procedures and CNI were the backbone of nearly all regimens with > 90% of recipients receiving tacrolimus or cyclosporine at the time of initial discharge.

CTOT-15 is designed to be a first step in providing the potential benefits of an immunosuppressive regimen based on an agent other than a CNI to this underserved patient population. Currently, SPK recipients have no alternatives to CNIs for maintenance immunotherapy. As a result, immunosuppressive protocols remain dependent on these agents despite the long term nephrotoxicity and beta cell toxicity associated with these agents. Furthermore, as abatacept, a precursor of NULOJIX® (belatacept), has been shown effective for treatment of the autoimmune disease psoriasis, we believe that NULOJIX® (belatacept) may offer unique benefits to pancreas transplant recipients with type I diabetes mellitus by acting to control the autoimmune response.

CTOT-15 will also incorporate a battery of mechanistic assays that are designed to be integrated with many of the assays being performed as part of CTOTC-02 and CTOT-16. These assays compare the effects of the belatacept-based regimen on protective antiviral immunity, alloimmunity, and autoimmunity. The study design allows us to focus on how these two different classes of immunosuppressive agents affect memory responses including those that predate the transplant and those arising from homeostatic lymphocyte repopulation.

Over the last two decades, the short-term results of organ transplantation have improved steadily in large part due to the introduction of increasingly potent immunosuppressants. Calcineurin inhibitors (CNI), such as cyclosporine and tacrolimus, form the backbone of the vast majority of all immunosuppressive regimens currently used in abdominal organ transplantation (www.srtr.org). The success of these CNI-based regimens is demonstrated by the ever-decreasing incidence of acute rejection and the ever-improving 1-year graft survival following de novo renal and extra-renal transplantation. Disappointingly, this improvement in short-term outcomes has not resulted in concomitant improvements in long-term outcomes¹,². The major factors limiting the long-term survival of transplanted kidneys and kidney transplant recipients are the near universal development of

interstitial fibrosis and tubular atrophy (IFTA)³ and the extremely high incidence of cardiovascular disease in transplant recipients. This is particularly true for patients with type 1 diabetes undergoing simultaneous kidney and pancreas transplantation.

It is widely recognized that CNIs are major contributors to the principal causes of the poor longterm results that still plague transplantation - death from cardiovascular disease and posttransplant renal failure, be it of the transplant or native kidneys. In the case of renal transplantation, virtually all patients develop lesions of CNI-induced nephrotoxicity and accelerated renal dysfunction 3. The impact of CNI-induced renal dysfunction is underscored by the well-recognized association between preservation of renal function at one year and longterm graft survival⁴,⁵. In addition to their nephrotoxic properties, CNIs are associated with a number of toxicities that increase the risk of death from cardiovascular disease, a factor that accounts for 45.7% of all graft losses following renal transplantation (USRDS Annual Report 1999). Most importantly, CNI are major contributors to the development of new onset diabetes mellitus (DM), the incidence of which approaches 30% following renal and 20% following liver transplantation ⁶,⁷,⁸. These data suggest that CNI would also have a negative impact on beta cell function following pancreas transplantation, although SPK recipients remain largely dependent on these agents to prevent rejection. Strikingly, new onset DM after renal transplantation is associated with more than a 60% increase in risk of graft failure and an almost 90% increase in risk of death⁹. CNI also cause and exacerbate hypertension and dyslipidemia, both of which are known to accelerate cardiovascular disease¹⁰. Together, these toxicities provide a compelling rationale for the identification of immunosuppressive agents that can replace CNI in maintenance immunosuppressive regimens following SPK.

The importance of developing regimens less dependent upon CNI is reflected in the large number of studies in renal transplantation designed to avoid or replace CNI with less toxic immunosuppressive drugs. That said, until the recent experience with belatacept identifying effective CNI alternatives has proven difficult. For example, attempts to use daclizumab, MMF and prednisone based regimens to spare CNI have been associated with excessive rates of ACR ¹¹, ¹². Similarly, attempts to use sirolimus as a CNI replacement have proven less than ideal. In the recent SYMPHONY trial, low-dose sirolimus in combination with Zenapax® (daclizumab) induction, MMF and prednisone was inferior to low-dose tacrolimus with respect to GFR, the incidence of ACR and the 1-year graft survival. Intermediate results were obtained in patients treated with low-dose CsA¹³. These data suggest that replacement of CNI with Rapamune® (sirolimus), as a means of avoiding the CNI toxicity may not improve the survival or function of renal grafts and likely not provide adequate immunoprotection for SPK subjects.

Corticosteroids, another widely used class of immunosuppressive agents, are also associated with a myriad of metabolic and cardiovascular side effects reported to include weight gain, hypertension, glucose intolerance, abnormalities of lipids, cardiovascular and bone disease to name a few. Several immunosuppressive regimens have been reported that avoid steroids thereby achieving favorable changes in metabolic profiles while simultaneously achieving acceptably low rates of rejection. These have most frequently used either Thymoglobulin® (anti-thymocyte globulin) or Campath® (alemtuzumab) for induction and Prograf® (tacrolimus) and CellCept® (mycophenolate mofetil-MMF) for maintenance immunosuppression.

While the potential advantages of minimizing or avoiding both CNI and corticosteroids are both obvious and significant, to date there are no large randomized, prospective, multicenter studies

demonstrating either the efficacy or the safety of immunosuppressive regimens that avoid both CNI and corticosteroids following kidney and/or pancreas transplantation.

NULOJIX® (BELATACEPT) IN TRANSPLANTATION

One promising approach to avoid chronic therapy with CNI is to use the biologic immunosuppressive drug NULOJIX® (belatacept). Belatacept is a new class of immunosuppressive therapy for transplantation. It is a fusion protein that binds to the B7 molecules on the surface of antigen-presenting cells (APCs) inhibiting the delivery of CD28-dependent co-stimulation for T-cell activation. Belatacept differs from existing immunosuppressants in the restricted distribution of its molecular target and the specificity of its effect. It is administered via intravenous infusion. In the phase II and III, studies it has been given monthly during the maintenance phase for up to six years post-transplant.

Belatacept is a soluble chimeric protein designed to selectively inhibit costimulation of T-cells. T-cells require 2 signals for activation. The first signal, which is antigen specific, is delivered by engagement of the T-cell receptor (TCR) with antigen presented in context with major histocompatibility complex molecules on the APC. The second, or co-stimulatory signal, is delivered by engagement of co-stimulatory ligand on the APC with a receptor on the T-cell. A key co-stimulatory signal is provided by the interaction of B7-1 (CD80) and B7-2 (CD86) on APCs with CD28 expressed on T-cells. In the absence of this second signal, the T-cell becomes anergic (unresponsive) or undergoes apoptosis.

Conversely, if the T-cell becomes fully activated, CTLA4 (CD152) becomes expressed on the cell surface. CTLA4 has a substantially higher avidity than CD28 for CD80 and CD86 (approximately 500-to 2,500-fold). The increased avidity of endogenous CTLA4, in comparison with CD28, affords a homeostatic mechanism to down-regulate T-cell activity.

Belatacept was derived from CTLA4Ig (Abatacept, BMS-188667), a novel fusion protein consisting of the extracellular domain of human CTLA4 fused to a fragment of the Fc domain of a human immunoglobulin (Ig) G1 antibody. By binding avidly to CD80/86, CTLA4Ig blocks the interaction of the T-cell's CD28 with the APCs CD80/CD86, thus preventing T-cells from receiving the required second costimulatory signal. CTLA4Ig has been shown to be efficacious in a wide variety of preclinical models and in participants with psoriasis and rheumatoid arthritis. With respect to transplantation, CTLA4Ig demonstrated efficacy in rodent models of transplantation, but did not demonstrate substantial efficacy in non-human primate models (cynomolgus monkeys). Therefore belatacept, a 2 amino acid variant of CTLA4Ig was developed. This alteration resulted in markedly increased binding avidity for B7 molecules. Belatacept was subsequently shown to have efficacy in non-human primate renal transplant model in which CTLA4Ig was not efficacious⁷. Belatacept was also shown to be efficacious in Phase 2 clinical trial in de novo renal transplant recipients (Study IM103-100).

